Appendix 3 Management of Cobimetinib plus Atezolizumab–Associated Adverse Events (Arm A) (cont.)

Table 3 Guidelines for Managing Atezolizumab and Cobimetinib Rash (cont.)

Dermatologic Toxicity/Rash (e.g., maculo-papular or purpura)	Management
Dermatologic event, Grade 4	Permanently discontinue all study treatment and contact Medical Monitor.

BID = twice daily; BSA = body surface area; PRN = as needed.

- ^a If corticosteroids have been initiated, they must be tapered over ≥ 1 month to ≤ 10 mg/day oral prednisone or equivalent before atezolizumab can be resumed.
- ^b Atezolizumab may be withheld for a period of time beyond 12 weeks to allow for corticosteroids to be reduced to ≤ 10 mg/day oral prednisone or equivalent. The acceptable length of the extended period of time must be agreed upon by the investigator and the Medical Monitor.
- ^c Resumption of atezolizumab may be considered in patients who are deriving benefit and have fully recovered from the immune-related event. Patients can be rechallenged with atezolizumab only after approval has been documented by both the investigator (or an appropriate delegate) and the Medical Monitor.

PULMONARY TOXICITY

Mild-to-moderate events of pneumonitis have been reported with atezolizumab and cobimetinib. All pulmonary events should be thoroughly evaluated for other commonly reported etiologies such as pneumonia/infection, lymphangitic carcinomatosis, pulmonary embolism, heart failure, chronic obstructive pulmonary disease, or pulmonary hypertension.

Pulmonary toxicity should be managed per the guidelines in [Table 4](#).

Appendix 3 Management of Cobimetinib plus Atezolizumab–Associated Adverse Events (Arm A) (cont.)

Table 4 Guidelines for Managing Atezolizumab– and Cobimetinib–Associated Pulmonary Toxicity

Pulmonary Toxicity	Management
General Guidance	
Mild-to-moderate events of pneumonitis have been reported with atezolizumab and cobimetinib. All pulmonary events should be thoroughly evaluated for other commonly reported etiologies such as pneumonia/infection, lymphangitic carcinomatosis, pulmonary embolism, heart failure, chronic obstructive pulmonary disease, or pulmonary hypertension.
 
For events concerning for pneumonitis, Consider comprehensive infectious evaluation including viral etiologies.

Pneumonitis, Grade 1 (asymptomatic)	
Continue atezolizumab and cobimetinib.
 
Re-evaluate on serial imaging.
 
Consider patient referral to pulmonary specialist.
 
For recurrent pneumonitis, treat as Grade 3 or 4 event.

Pneumonitis, Grade 2	
Withhold atezolizumab and cobimetinib.
 
Refer patient to pulmonary and infectious disease specialists and consider bronchoscopy or BAL.
 
If bronchoscopy is consistent with immune-mediated etiology, initiate treatment with 1–2 mg/kg/day oral prednisone or equivalent.
 
Resume atezolizumab and cobimetinib if event resolves to Grade 1 or better within 12 weeks.^{a, b}
 
Permanently discontinue atezolizumab and contact Medical Monitor if event does not resolve to Grade 1 or better within 12 weeks.^{a, b, c}
 
For recurrent events, treat as a Grade 3 or 4 event.

Appendix 3 Management of Cobimetinib plus Atezolizumab–Associated Adverse Events (Arm A) (cont.)

Table 4 Guidelines for Managing Atezolizumab– and Cobimetinib–Associated Pulmonary Toxicity (cont.)

Pulmonary Toxicity	Management
Pneumonitis, Grade 3/4	
Permanently discontinue atezolizumab and cobimetinib.^c
 
Refer patient to pulmonary and infectious disease specialists and consider bronchoscopy or BAL.
 
If bronchoscopy is consistent with immune-related etiology, initiate treatment with 1–2 mg/kg/day oral prednisone or equivalent.
 
If pulmonary event does not improve within 48 hr or worsens, consider adding an immunosuppressive agent (e.g., infliximab, cyclophosphamide, IV Ig, or mycophenolate mofetil).
 
If event resolves to Grade 1 or better, taper corticosteroids over ≥ 1 month.

IV =intravenous; GGO =ground glass opacity.

^a If corticosteroids have been initiated, they must be tapered over ≥ 1 month to ≤ 10 mg/day oral prednisone or equivalent before atezolizumab can be resumed.

^b Atezolizumab may be withheld for a period of time beyond 12 weeks to allow for corticosteroids to be reduced to ≤ 10 mg/day oral prednisone or equivalent. The acceptable length of the extended period of time must be agreed upon by the investigator and the Medical Monitor.

^c Resumption of atezolizumab may be considered in patients who are deriving benefit and have fully recovered from the immune-related event. Patients can be rechallenged with atezolizumab only after approval has been documented by both the investigator (or an appropriate delegate) and the Medical Monitor.

POTENTIAL EYE TOXICITY

An ophthalmologist should evaluate visual complaints.

Uveitis or episcleritis and other immune-mediated ocular disease may be associated with atezolizumab and may be treated with topical corticosteroid eye drops. Atezolizumab should be permanently discontinued for immune-mediated ocular disease that is unresponsive to local immunosuppressive therapy.

Atezolizumab-associated ocular toxicity should be managed according to the guidelines in [Table 5](#).

Serous retinopathy is associated with cobimetinib. In clinical trials, most events were Grade 1 (asymptomatic) or 2 (symptomatic). Most events in clinical trials resolved or improved to asymptomatic grade 1 following dose interruption or reduction. If serous retinopathy is diagnosed, cobimetinib should be withheld until visual symptoms improve to Grade ≤ 1 . Serous retinopathy can be managed with treatment interruption, dose reduction or with treatment discontinuation.

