5.1.1.1 Important Identified Risks Associated with Cobimetinib Hemorrhage

Hemorrhage, including major hemorrhages defined as symptomatic bleeding in a critical area or organ, can occur with cobimetinib. In clinical studies with cobimetinib, events of cerebral hemorrhage, gastrointestinal tract hemorrhage, reproductive tract hemorrhage, and hematuria, have been reported.

In the Phase III Study GO28141, Grade 1–4 hemorrhagic events were reported in 13.0% of patients treated with cobimetinib plus vemurafenib, and in 7.3% of patients treated with placebo plus vemurafenib. The majority of hemorrhagic events were Grade 1 or 2 and non-serious. Grade 3–4 hemorrhage events were reported in 1.2% of patients receiving cobimetinib plus vemurafenib and 0.8% of patients receiving placebo plus vemurafenib.

Caution should be used in patients with additional risk factors for bleeding, such as brain metastases, and/or in patients that use concomitant medications that increase the risk of bleeding (including antiplatelet or anticoagulant therapy).

Instructions for dose modification for hemorrhage events are included in [Appendix 3](#).

Serous Retinopathy

Serous retinopathy (fluid accumulation within the layers of the retina) has been observed in patients treated with MEK-inhibitors, including cobimetinib ([Flaherty et al. 2012](#)). Manifestations of serous retinopathy include visual disturbances, findings of retinal detachment, and retinopathy. Serous retinopathy events may also be asymptomatic.

Serous retinopathy has been characterized in the Phase III Study GO28141. The study incorporated prospective serial ophthalmic examinations for all enrolled patients. Serous retinopathy was reported more frequently in patients treated with cobimetinib plus vemurafenib than placebo plus vemurafenib (25.5% vs. 2.8%, respectively), and approximately half the events were asymptomatic Grade 1 events. Few patients treated with cobimetinib plus vemurafenib experienced Grade ≥ 3 ocular events (2.8%); the majority of these were managed with dose modification of both cobimetinib and vemurafenib.

To address serous retinopathy with cobimetinib treatment, all patients are required to undergo a baseline ophthalmologic examination to assess for history or evidence of

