retinal pathology that is considered to be a risk factor for or indicative of neurosensory retinal detachment, central serous chorioretinopathy, neovascular retinopathy, or retinopathy of prematurity. Patients will also undergo ophthalmologic examinations at specified time points throughout the study (see [Appendix 1](#)). Details regarding baseline and subsequent ophthalmologic examinations are provided in [Appendix 3](#).

Guidelines for management of patients who develop Grade ≥ 2 visual disorders or retinopathy are provided in [Appendix 3](#).

Left Ventricular Dysfunction

Decrease in left ventricular ejection fraction from baseline has been reported in patients receiving cobimetinib. Left ventricular dysfunction may occur with signs and symptoms of cardiac failure, or reduction in left ventricular ejection fraction events may be asymptomatic.

Left ventricular dysfunction has been characterized in the Phase III Study GO28141. The study incorporated prospective serial left ventricular ejection fraction evaluation in all patients. With active surveillance, measured reductions in left ventricular ejection fraction were observed more frequently in patients treated with cobimetinib plus vemurafenib than placebo plus vemurafenib (8.5% vs. 3.7%, respectively, of Grade 2 or 3 decrease). Of the patients treated with cobimetinib plus vemurafenib, 2 patients (0.8%) had symptomatic reduction in left ventricular ejection fraction and the remaining patients were asymptomatic. Most left ventricular ejection fraction reduction events in patients on cobimetinib plus vemurafenib (62%) improved or resolved with management according to the dose-modification guidelines (see [Appendix 3](#)).

Rhabdomyolysis and CPK Elevations

Elevations in CPK have been observed in patients who received cobimetinib monotherapy as well as when administered with other agents. The majority of CPK elevations reported were asymptomatic, non-serious, and resolved with or without study drug interruption. One event of rhabdomyolysis was reported in the Phase III Study GO28141 (cobimetinib plus vemurafenib), and rhabdomyolysis has been reported in postmarketing experience.

In Study GO28141, elevated CPK was reported as an adverse event more frequently in patients treated with cobimetinib plus vemurafenib (32.4% all grades, 11.3% Grade ≥ 3 events) than placebo plus vemurafenib (8.1% all grades, 0% Grade ≥ 3 events).

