5.1.4.1 **Cobimetinib and Regorafenib Dose Modifications**

Cobimetinib and regorafenib dose modifications are provided in [Table 3](#).

Table 3 Recommended Cobimetinib and Regorafenib Dose Modifications

Grade (CTCAE) ^a	Recommended Cobimetinib Dose	Recommended Regorafenib Dose
Grade 1 or Grade 2 (tolerable)	No dose reduction. Maintain cobimetinib at the same dose of 60 mg QD (3 tablets)	No dose reduction. Maintain regorafenib at the same dose of 160 mg QD (4 tablets)
Grade 2 (intolerable) or Grade 3 or 4 (any)		
First appearance	Interrupt treatment until Grade ≤ 1 , restart treatment at 40 mg QD (2 tablets)	Interrupt treatment until Grade ≤ 1 , restart treatment at 120 mg QD (3 tablets)
Second appearance	Interrupt treatment until Grade ≤ 1 , restart treatment at 20 mg QD (1 tablet)	Interrupt treatment until Grade ≤ 1 , restart treatment at 80 mg QD (2 tablets)

Grade (CTCAE) ^a	Recommended Cobimetinib Dose	Recommended Regorafenib Dose
Third appearance	Consider permanent discontinuation	Consider permanent discontinuation

CTCAE = Common Terminology Criteria for Adverse Events; NCI = National Cancer Institute; QD = once daily.

^a The intensity of clinical adverse events graded by NCI CTCAE v4.0.

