Appendix 3 Management of Cobimetinib plus Atezolizumab–Associated Adverse Events (Arm A) (cont.)

Retinal vein occlusion (RVO) has been reported in patients treated with MEK inhibitors other than cobimetinib.

Cobimetinib–associated ocular toxicity should be managed according to the guidelines in [Table 6](#).

Table 5 Guidelines for Managing Atezolizumab–Associated Ocular Toxicity (Immune–Mediated Ocular Disease)

Description	Management
Potential immune-related ocular toxicity (e.g., uveitis, iritis, episcleritis, or retinal events)	Follow guidelines provided in the Appendix 9 . Continue cobimetinib as clinically indicated.

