Appendix 3 Management of Cobimetinib plus Atezolizumab–Associated Adverse Events (Arm A) (cont.)

Table 6 Guidelines for Managing Cobimetinib-Associated Serous Retinopathy and Retinal Vein Occlusion

Description	Management

Serous retinopathy
 
Severity grade assessment based on NCI CTCAE v4 “Eye Disorders – Other” scale ^{a-d}
	
Serous retinopathy, Grade 1 ^a or 2 ^b (tolerable):
 
 • Continue cobimetinib and atezolizumab without dose change. • Continue ophthalmology follow-up as clinically indicated. 
Serous retinopathy, Grade 2 ^b (intolerable) or 3/4 ^{c/d}:
 
 • Interrupt cobimetinib until Grade \leq 1. • Continue atezolizumab as clinically indicated. • Consult ophthalmology and undergo complete ophthalmologic examination, which includes visual acuity testing, intra-ocular pressure measurements, slit lamp ophthalmoscopy, indirect ophthalmoscopy, visual field, and OCT. Consider a fluorescein angiogram and/or indocyanine green angiogram, if clinically indicated. • Cobimetinib should be dose reduced by 1 dose level when restarting. • Consider permanent discontinuation of cobimetinib if serous retinopathy recurs despite 2 dose level reductions

Retinal vein occlusion
 
Any grade
	
If RVO (any grade) is diagnosed, cobimetinib dosing should be permanently discontinued and RVO treated per institutional guidelines.
 
Continue atezolizumab.

ADL = activities of daily living; NCI CTCAE = National Cancer Institute Common Terminology Criteria for Adverse Events; RVO = retinal vein occlusion; OCT = optical coherence tomography.

^a Grade 1: Asymptomatic or mild symptoms; clinical or diagnostic observations only; intervention not indicated.

^b Grade 2: Moderate; minimal, local or noninvasive intervention indicated; limiting age appropriate instrumental ADL.

^c Grade 3: Severe or medically significant but not immediately sight threatening; hospitalization or prolongation of existing hospitalization indicated; disabling; limiting self-care ADL.

^d Grade 4: Sight-threatening consequences; urgent intervention indicated; blindness (20/200 or worse) in the affected eye.

GUIDELINES FOR MANAGEMENT OF PATIENTS WHO EXPERIENCE DECREASED LEFT VENTRICULAR EJECTION FRACTION

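### Appendix 3 tells sites both to withhold and to continue cobimetinib for tolerable Grade 2 serous retinopathy

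*Protocol*

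**What the plan says.** Protocol Appendix 3 covers Arm A. Under Potential Eye Toxicity, the narrative before the tables says: "If serous retinopathy is diagnosed, cobimetinib should be withheld until visual symptoms improve to Grade" 1 or lower. The trigger is the diagnosis, with no entry grade. The same paragraph labels Grade 1 asymptomatic and Grade 2 symptomatic. It then lists interruption, reduction and discontinuation as ways to manage the event; continuing unchanged is not among them.

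A little further on, the appendix says that cobimetinib-associated "ocular toxicity should be managed according to the guidelines in" Table 6. That table has two rows for serous retinopathy:

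- Grade 1 or tolerable Grade 2: "Continue cobimetinib and atezolizumab without dose change", with ophthalmology follow-up.
- Intolerable Grade 2 or Grade 3/4: interrupt until Grade 1 or lower. For this row only: "Cobimetinib should be dose reduced by 1 dose level when restarting".

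Two places in the body of the protocol bear on this. Section 5.1.1.1 (Serous Retinopathy) refers Grade 2 and above to Appendix 3 in general, not to Table 6. Table 3 in Section 5.1.4.1, the general dose-modification table, keeps cobimetinib at 60 mg for any tolerable Grade 2 event.

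**The concern.** A site with a patient who has tolerable Grade 2 serous retinopathy cannot follow both instructions, since one stops cobimetinib and the other continues it at full dose. A site that does withhold then has no restart dose for this patient. The one-level reduction in Appendix 3 Table 6 belongs to the intolerable Grade 2 or Grade 3/4 row, and the interrupt-and-reduce steps in Table 3 of Section 5.1.4.1 are confined to the same grades. Restarting at 60 mg and at 40 mg are both defensible.

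Serous retinopathy of any grade is an adverse event of special interest (Section 5.2.3), and Arm A has scheduled eye examinations (Section 4.5.9), so cases will be looked for. With about 75 centers (Section 9.4), practice could differ between sites. That would feed into the Arm A summaries of dose intensity and of adverse events leading to interruption (protocol Section 6.6; SAP Sections 4.6.1 and 4.6.2). Whichever rule a site follows, it departs from one current instruction.

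**Working it through.** **Comparison by grade.** No design figure in the plan is involved, so the check sets the two instructions side by side.

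| Grade | Narrative | Appendix 3 Table 6 | Result |
|---|---|---|---|
| 1 | Withhold until Grade ≤ 1; condition already met, so no effective hold | Continue | No practical conflict |
| 2, tolerable | Withhold until Grade ≤ 1 | Continue, no dose change | **Conflict** |
| 2, intolerable | Withhold until Grade ≤ 1 | Interrupt until Grade ≤ 1 | Agree |
| 3 or 4 | Withhold until Grade ≤ 1 | Interrupt until Grade ≤ 1 | Agree |

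Only tolerable Grade 2 conflicts.

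**How many patients could be in that cell.** The inputs are from Section 5.1.1.1 and describe cobimetinib plus vemurafenib in Study GO28141:

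- serous retinopathy in 25.5% of patients;
- "approximately half the events were asymptomatic Grade 1 events";
- Grade ≥ 3 ocular events in 2.8% of patients.

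Arm A has about 180 patients (Section 3.1). Grade 2 is taken as what is left:

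Grade 2 = all cases − asymptomatic Grade 1 − Grade ≥ 3

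At the full rate:

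- all cases: 0.255 × 180 = 45.9
- asymptomatic Grade 1: 45.9 / 2 = 22.95
- Grade ≥ 3: 0.028 × 180 = 5.04
- Grade 2: 45.9 − 22.95 − 5.04 = 17.9, about 10% of Arm A

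At half the rate (an assumption, to allow for a different partner drug):

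- all cases 22.95, asymptomatic Grade 1 11.5, Grade ≥ 3 2.5
- Grade 2: about 9.0, or 5.0% of Arm A

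The documents do not say what share of Grade 2 is tolerable, so the whole range is shown:

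| Tolerable share of Grade 2 | Full rate | Half rate |
|---|---|---|
| 0% | 0 | 0 |
| 25% | 4.5 | 2.2 |
| 50% | 9.0 | 4.5 |
| 75% | 13.4 | 6.7 |
| 100% | 17.9 | 9.0 |

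**Dose at stake on restart.** One dose level is 60 mg to 40 mg (Table 3, Section 5.1.4.1).

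**The case against.** The strongest reply is that the protocol already resolves this. The sentence sits in a short narrative about trial experience. The appendix then directs management to Table 6, which is graded and carries its own grade definitions, and the general dose table independently gives the same answer. The reference in Section 5.1.1.1 leads to the same place, because Appendix 3 itself points to Table 6. The missing restart dose arises only for a site that sets Table 6 aside.

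Much of this stands. It shows which text is intended, and it makes the restart gap a consequence of the conflict, not a separate fault. It does not remove the conflict. The sentence has its own trigger and release threshold and reads as an instruction, and no text ranks the table above it. A reader sent to Appendix 3 meets the hold before the table.

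The counts are also open to challenge. They mix a patient percentage, a share of events and a rate for Grade ≥ 3 ocular events of any kind, and they come from a different combination. Table 6 counts mild symptoms as Grade 1, so the Grade 2 remainder may be too high. The counts describe patients for whom the instructions differ, not patients actually managed differently; zero is realistic. These limits are accepted, and the conflict does not depend on the estimate.

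The consequences are cushioned as well: eye monitoring continues under either rule, and events of special interest reach the sponsor within 24 hours.

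**Conclusion.** The concern holds. Two current instructions in Appendix 3 contradict each other for tolerable Grade 2 serous retinopathy and for no other grade. Table 6 is the likely intended rule.

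The size is 0 to about 18 Arm A patients (0 to 10%), or 0 to about 9 (0 to 5%) at half the rate. If half of Grade 2 cases are tolerable, the figures are about 9 and about 4 to 5. This assumes that the vemurafenib-combination experience is a usable guide; both the half-rate case and the 50% share are assumptions. Confidence is high on the contradiction and low on the counts.

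The effect is confined to Arm A cobimetinib dosing, safety conduct and descriptive exposure and interruption summaries. The overall survival comparison, alpha, power and number of deaths are unaffected. It should be corrected because it is a contradictory dosing rule for a known toxicity, not because it threatens the trial's conclusions.

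**What to change.** Replace the narrative sentence in Appendix 3 with one that carries an entry grade and names the table, for example: *For serous retinopathy of intolerable Grade 2, or of Grade 3 or higher, hold cobimetinib until the event is Grade ≤ 1, then follow Table 6.* Leave Table 6 as it is. The narrative then matches both graded tables, and the restart question for tolerable Grade 2 disappears because no hold is called for.

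The cost is one sentence in the next amendment and a short notice to sites.

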Appendix 3 Management of Cobimetinib plus Atezolizumab–Associated Adverse Events (Arm A) (cont.)

Retinal vein occlusion (RVO) has been reported in patients treated with MEK inhibitors other than cobimetinib.

Cobimetinib–associated ocular toxicity should be managed according to the guidelines in [Table 6](#).

Table 5 Guidelines for Managing Atezolizumab–Associated Ocular Toxicity (Immune–Mediated Ocular Disease)

Description	Management
Potential immune-related ocular toxicity (e.g., uveitis, iritis, episcleritis, or retinal events)	Follow guidelines provided in the Appendix 9 . Continue cobimetinib as clinically indicated.

Appendix 3 Management of Cobimetinib plus Atezolizumab–Associated Adverse Events (Arm A) (cont.)

Table 6 Guidelines for Managing Cobimetinib-Associated Serous Retinopathy and Retinal Vein Occlusion

Description	Management

Serous retinopathy
 
Severity grade assessment based on NCI CTCAE v4 “Eye Disorders – Other” scale ^{a-d}
	
Serous retinopathy, Grade 1 ^a or 2 ^b (tolerable):
 
 • Continue cobimetinib and atezolizumab without dose change. • Continue ophthalmology follow-up as clinically indicated. 
Serous retinopathy, Grade 2 ^b (intolerable) or 3/4 ^{c/d}:
 
 • Interrupt cobimetinib until Grade \leq 1. • Continue atezolizumab as clinically indicated. • Consult ophthalmology and undergo complete ophthalmologic examination, which includes visual acuity testing, intra-ocular pressure measurements, slit lamp ophthalmoscopy, indirect ophthalmoscopy, visual field, and OCT. Consider a fluorescein angiogram and/or indocyanine green angiogram, if clinically indicated. • Cobimetinib should be dose reduced by 1 dose level when restarting. • Consider permanent discontinuation of cobimetinib if serous retinopathy recurs despite 2 dose level reductions

Retinal vein occlusion
 
Any grade
	
If RVO (any grade) is diagnosed, cobimetinib dosing should be permanently discontinued and RVO treated per institutional guidelines.
 
Continue atezolizumab.

ADL = activities of daily living; NCI CTCAE = National Cancer Institute Common Terminology Criteria for Adverse Events; RVO = retinal vein occlusion; OCT = optical coherence tomography.

^a Grade 1: Asymptomatic or mild symptoms; clinical or diagnostic observations only; intervention not indicated.

^b Grade 2: Moderate; minimal, local or noninvasive intervention indicated; limiting age appropriate instrumental ADL.

^c Grade 3: Severe or medically significant but not immediately sight threatening; hospitalization or prolongation of existing hospitalization indicated; disabling; limiting self-care ADL.

^d Grade 4: Sight-threatening consequences; urgent intervention indicated; blindness (20/200 or worse) in the affected eye.

GUIDELINES FOR MANAGEMENT OF PATIENTS WHO EXPERIENCE DECREASED LEFT VENTRICULAR EJECTION FRACTION

Decreased left ventricular ejection fraction (LVEF) has been seen with cobimetinib (see Section 5.1.1.1). Refer to [Table 7](#) for guidelines for management of LVEF. Permanent discontinuation of cobimetinib treatment should be considered if cardiac symptoms are attributed to cobimetinib and do not improve after temporary interruption.

